6.2 Nonserious Adverse Events

A **nonserious AE** is an AE not classified as SAE.

6.2.1 Nonserious Adverse Event Collection and Reporting

The collection of nonserious AE information should begin at initiation of study drug. Nonserious AE information should also be collected from the start of a placebo lead-in period or other observational period intended to establish a baseline status for the subjects.

Nonserious AEs should be followed to resolution or stabilization, or reported as SAEs if they become serious (see [Section 6.1.1](#)). Follow-up is also required for nonserious AEs that cause interruption or discontinuation of study drug and for those present at the end of study treatment as appropriate. All identified nonserious AEs must be recorded and described on the nonserious AE page of the CRF (paper or electronic).

Completion of supplemental CRFs may be requested for AEs and/or laboratory abnormalities that are reported/identified during the course of the study.

6.3 Adverse Events of Special Interest

Adverse events of special interest (AEOSI) have been defined for this protocol which require expedited reporting by the investigator of these adverse events to BMS. These are:

- Hemophagocytic lymphohistiocytosis (HLH; also known as histiocytosis haematophagic)
- Drug reaction with eosinophilia and systemic symptoms (DRESS) syndrome

These AEOSI, whether related or not related to study drug, must be reported to BMS or designee within 24 hours of awareness of the event. These AEOSI are medically important events and are therefore considered SAEs. The reporting system for SAEs should be used (see [Section 6.1.1](#)).

Both HLH and DRESS syndrome may both pose diagnostic challenges due to varying clinical manifestations and signs and symptoms that may overlap with other clinical events. To assist investigators in identifying constellations of clinical symptoms that may be consistent with one of these diagnoses, standardized scoring criteria are provided in [Appendix 12](#). Formal evaluation and documentation of diagnostic scores based on these systems is not required; investigators should use their best clinical judgement as informed by these provided criteria to determine if a subject has experienced one of these AEOSI.

6.4 Laboratory Test Result Abnormalities

The following laboratory test result abnormalities should be captured on the nonserious AE CRF page or SAE Report Form (paper or electronic) as appropriate:

- Any laboratory test result that is clinically significant or meets the definition of an SAE
- Any laboratory test result abnormality that required the subject to have study drug discontinued or interrupted
- Any laboratory test result abnormality that required the subject to receive specific corrective therapy

It is expected that wherever possible, the clinical rather than laboratory term would be used by the reporting investigator (eg, anemia versus low hemoglobin value).

6.5 Pregnancy

If, following initiation of the investigational product, it is subsequently discovered that a study subject is pregnant or may have been pregnant at the time of study exposure, including during at least 5 half-lives + 30 days after nivolumab administration (for a total of 23 weeks post-treatment

completion), the investigator must immediately notify the BMS Medical Monitor/designee of this event and complete and forward a Pregnancy Surveillance Form to the BMS designee within 24 hours of awareness of the event and in accordance with SAE reporting procedures described in [Section 6.1.1](#).

In most cases, the study drug will be permanently discontinued in an appropriate manner (eg, dose tapering if necessary for subject safety).

If the investigator determines a possible favorable benefit/risk ratio that warrants continuation of study treatment, or re-initiation of study treatment, a discussion between the investigator and the BMS Medical Monitor/designee must occur. If, for whatever reason, the pregnancy has ended, confirmed by negative serum pregnancy test, treatment may be resumed (at least 3 weeks and not greater than 6 weeks after the pregnancy has ended), following approvals of subject /sponsor /IRB/EC, as applicable.

Follow-up information regarding the course of the pregnancy, including perinatal and neonatal outcome, and where applicable, offspring information must be reported on the Pregnancy Surveillance Form.

Any pregnancy that occurs in a female partner of a male study subject should be reported to BMS. Information on this pregnancy will be collected on the Pregnancy Surveillance Form.

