3.5 Discontinuation of Subjects Following any Treatment with Study Drug

Subjects MUST discontinue investigational product (and non-investigational product at the discretion of the investigator) for any of the following reasons:

- Subject's request to stop study treatment and/or participation in the study
- Any clinical AE, laboratory abnormality or intercurrent illness that in the opinion of the investigator indicates that continued participation in the study is not in the best interest of the subject
- Termination of the study by BMS
- Loss of ability to freely provide consent through imprisonment or involuntarily incarceration for treatment of either a psychiatric or physical (eg, infectious disease) illness
- Inability to comply with protocol
- Discretion of the investigator
- Pregnancy
- Completion of study-required procedures.
- Documented and confirmed disease progression as defined by RECIST v1.1 or IWG (see [Appendix 3](#) and [4](#)) unless subject meets criteria for treatment beyond progression ([Section 3.5.1](#))
- Clinical deterioration while receiving active study drug that in the opinion of the investigator indicates that continued participation in the study is not in the best interest of the subject
- Protocol-defined reasons for discontinuation (see Sections 3.5.1 and [4.5.6](#)).

In the case of pregnancy, the investigator must immediately, within 24 hours of the event, notify the BMS Medical Monitor/designee of this event. In most cases, the study drug will be permanently discontinued in an appropriate manner. If the investigator determines a possible favorable benefit/risk ratio that warrants continuation of study drug, a discussion between the investigator and the BMS Medical Monitor/designee must occur.

All subjects who discontinue investigational product should comply with protocol-specified follow-up procedures as outlined in [Section 5](#). The only exception to this requirement is when a subject withdraws consent for all study procedures including post-treatment study follow-up or loses the ability to consent freely (ie, is imprisoned or involuntarily incarcerated for the treatment of either a psychiatric or physical illness).

If study drug is discontinued prior to the subject's completion of the study, the reason for the discontinuation must be documented in the subject's medical records and entered on the appropriate CRF page.

3.5.1 *Treatment Beyond Progression*

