CBC with Differential and Platelets	X	X	X	X	X	Q2W Nivo dosing only		X	Predose.
LFT Assessments	X	X	X	X	X	Q2W Nivo dosing only		X	Predose; includes AST, ALT, total bilirubin, direct bilirubin (only if total bilirubin is elevated), alkaline phosphatase, and GGT (only when alkaline phosphatase is increased to ≥ Grade 2).

Table 5.1-3: On-treatment Procedural Outline (BMS-986205 + Nivolumab Part 1 Dose Escalation and Part 2 Dose Expansion)

Procedure	Cycle 1 (4 weeks)				Cycles 2+ (4 weeks)			End of Treatment ^{a,b,c}	Notes
	Day 1	Day 8	Day 15	Day 22	Day 1	Day 15 (±2 days)	Day 22 (+7 days) ^d		
Thyroid Function Tests	X				X			X	If collected at screening do not repeat on Cycle 1 Day 1. Collect every 2 cycles, predose, beginning with Cycle 3 Day 1 and at the end of treatment. To include TSH with reflex testing to free T3 and free T4 if TSH abnormal. Results should be examined by the investigator or appropriate designee within 48 hours of dose administration.
Pregnancy Test (WOCBP)	X		Q2W Nivo dosing only		X	Q2W Nivo dosing only		X	Serum or urine pregnancy test must be performed (urine pregnancy test: minimum sensitivity 25 IU/L or equivalent units of hCG) within 24 hours prior to administration of study drug. If pregnancy test is positive, hold all study drugs and perform confirmatory testing. If pregnancy is confirmed, permanently discontinue all study drug and immediately notify Sponsor per Section 6.5 .
Adverse Event Reporting and Concomitant Medication Assessments									
Concomitant Medication Assessments	X	X	X	X	X	Q2W Nivo dosing only	X	X	Review prior to dosing.

Table 5.1-3: On-treatment Procedural Outline (BMS-986205 + Nivolumab Part 1 Dose Escalation and Part 2 Dose Expansion)

Procedure	Cycle 1 (4 weeks)				Cycles 2+ (4 weeks)			End of Treatment ^{a,b,c}	Notes
	Day 1	Day 8	Day 15	Day 22	Day 1	Day 15 (±2 days)	Day 22 (+7 days) ^d		
Monitor for Nonserious Adverse Events	X	X	X	X	X	Q2W Nivo dosing only	X	X	Nonserious AEs will be collected starting with the first dose of study drug and through 100 days after discontinuation of nivolumab.
Monitor for Serious Adverse Events	X	X	X	X	X	Q2W Nivo dosing only	X	X	All SAEs must be collected from the date of subject's written consent until 100 days post discontinuation of nivolumab or subject's participation in the study if the last scheduled visit occurs at a later time. eSAEs should be approved in the BMS EDC tool within 5 business days of entry.
Sample Collection									

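### Sections 3.5 and 6.5 contemplate continued study drug in pregnancy without excluding BMS-986205, against Section 1.4.2, the Section 3.5 mandatory list and 11 table notes

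*Combined protocol and SAP*

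**What the plan says.** **Rules that say stop.** Section 1.4.2 reports a rat embryofetal study at two oral doses, 20 and 50 mg/kg/day, giving 5 and 14 times the exposure at the 100 mg clinical dose. Fetal loss and malformations rose with dose, and the section advises against giving BMS-986205 to pregnant women, with no exception. Section 3.5 opens its list with "Subjects MUST discontinue investigational product (and non-investigational product at the discretion of the investigator) for any of the following reasons", and pregnancy is on the list. The pregnancy-test notes in Section 5.1 require testing "within 24 hours prior to administration of study drug. If pregnancy test is positive, hold all study drugs and perform confirmatory testing", and then: "If pregnancy is confirmed, permanently discontinue all study drug and immediately notify Sponsor per" the cited section.

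**Text that qualifies them.** A later paragraph of Section 3.5 says "In most cases, the study drug will be permanently discontinued in an appropriate manner". It adds that if the investigator finds a possibly favourable benefit/risk ratio that "warrants continuation of study drug, a discussion between the investigator and the BMS Medical Monitor/designee must occur". Section 6.5 has the same default and the same opening, extended to re-initiation: "warrants continuation of study treatment, or re-initiation of study treatment, a discussion between the investigator and the BMS Medical Monitor/designee must occur". Section 6.5 applies to a subject who "is pregnant or may have been pregnant at the time of study exposure".

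**Resumption.** Once a pregnancy has ended, Section 6.5 says "treatment may be resumed (at least 3 weeks and not greater than 6 weeks after the pregnancy has ended"). This requires a negative serum test and the approvals of subject, sponsor and IRB/EC, as applicable.

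**The concern.** An investigator faced with a confirmed pregnancy finds two instructions. The table note says all study drug stops permanently. The section that the note cites for notifying the sponsor says that stopping is the usual course and that continuation can be raised with the Medical Monitor. For BMS-986205 the protocol's own toxicity section leaves nothing to weigh while the subject is pregnant, yet the two operative sections treat it like the other drugs. What is at stake is fetal exposure to a compound with a stated animal signal, and consistent conduct across sites. A second, smaller mismatch is that the notes' *permanently* cannot be followed together with a rule that allows resumption.

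**Working it through.** No arithmetic beyond a count applies, so the texts are set side by side.

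**1. Does the opening reach BMS-986205?**
- Section 3.5 speaks of study drug. Section 4 counts every protocol-specified investigational and non-investigational product as study drug.
- Section 4.1 names BMS-986205, nivolumab and ipilimumab as the investigational products.
- Section 6.5 speaks of study treatment. Section 4.5.4 spells that term out as the same three drugs.
- Neither Section 3.5 nor Section 6.5 carves BMS-986205 out. By definition it is included.

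**2. Does the parenthesis in the Section 3.5 list help?** It gives the investigator discretion over non-investigational product only. All three study agents are investigational under Section 4.1, so the mandatory wording applies to each of them.

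**3. How many table notes order a permanent stop?**
- On-treatment tables: 5.1-2, 5.1-3, 5.1-4, 5.1-5, 5.1-6, 5.1-14, 5.1-15 = 7.
- Re-treatment tables: 5.1-9, 5.1-10, 5.1-11, 5.1-12 = 4.
- Total 7 + 4 = 11 of 15 tables. The other four (5.1-1 screening, 5.1-7 follow-up, 5.1-8 re-treatment Day 0, 5.1-13 re-treatment follow-up) carry no such order.
- Ten of the 11 notes cite Section 6.5 and one (Table 5.1-9) cites Section 3.5, so every note leads to a section that contains the qualification.

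**4. Which subjects are in conflict with Section 1.4.2?**

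| Situation | Section 1.4.2 | Sections 3.5 / 6.5 | Conflict with 1.4.2? |
|---|---|---|---|
| Currently pregnant, BMS-986205 | Do not give | Continuation contemplated after discussion | Yes |
| Currently pregnant, nivolumab or ipilimumab | Silent | Continuation contemplated after discussion | No (but the table notes say stop) |
| Pregnancy ended | Silent | Resumption at 3 to 6 weeks, with conditions | No (but the notes say permanently) |
| May have been pregnant at exposure, not now | Silent | Covered by 6.5 | No |

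**5. Is there a rule of precedence?** None was found in the protocol. The conflict is in current text, and no redaction accounts for it.

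**The case against.** The best defence has four parts.

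- **A required discussion is not permission.** This stands. Neither section says that dosing may continue in pregnancy, whereas the resumption sentence does use permissive words. But both sections present continuation as a possible outcome for drugs that include BMS-986205.
- **The later paragraph of Section 3.5 elaborates its own list item.** It can be read as a specific qualifier of a general rule. That weakens the conflict within Section 3.5. It does not reconcile either section with Section 1.4.2 or the table notes.
- **The exception may be meant for the antibodies.** Table 4.5.3-1 already allows BMS-986205 to be stopped while nivolumab, with or without ipilimumab, continues, and cohort 6d receives nivolumab alone. Such a reading agrees with Section 1.4.2, but Sections 3.5 and 6.5 do not state it. The table shows how easily the drugs could have been separated here.
- **Safeguards surround the exception.** Stopping is the default, drug is held on a positive test, and Sections 3.5 and 6.5 require prompt notification of the sponsor. This limits the risk and leaves the contradiction in place.

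Some stronger readings are tempting and are not supported. A reader might infer that the protocol authorises dosing of pregnant subjects; it requires a discussion and goes no further. A reader might call the resumption rule unsafe and want it deleted; its conditions are a pregnancy that has ended, a negative serum test, the 3-to-6-week window and the applicable approvals. A reader might size the problem by the 14-, 21- or 28-day gaps between pregnancy tests; those describe exposure before detection, which this wording does not govern. A reader might contrast Appendix 11, which allows no exception for a male subject's pregnant partner; the partner is untreated and has no benefit to weigh, so the comparison shows little.

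**Conclusion.** The concern holds as an internal conflict of rules. For a currently pregnant subject, Section 1.4.2, the Section 3.5 list and 11 table notes say stop, while two passages leave continuation of BMS-986205 open to discussion. The separate mismatch between *permanently* and the resumption rule also holds.

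The size is modest. The documents report no human pregnancy outcome and give no basis for estimating how many subjects could be affected. No endpoint, analysis, sample size or error rate changes. It should still be fixed, because it concerns a stated fetal hazard and the remedy is small. The conclusion assumes that the definitions in Sections 4, 4.1 and 4.5.4 govern the terms used in Sections 3.5 and 6.5; nothing in the protocol suggests otherwise.

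**What to change.** 1. In Sections 3.5 and 6.5, state that BMS-986205 must be stopped on confirmed pregnancy and must not be continued or re-initiated while the subject is pregnant.
2. Limit any benefit/risk exception that the sponsor keeps to nivolumab and/or ipilimumab. If one is kept, change the all-study-drug wording in the 11 table notes to match. Whether to keep one is the sponsor's decision.
3. Amend *permanently* in the 11 notes to refer to the Section 6.5 resumption rule, and keep all of that rule's conditions.

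**Cost.** A protocol amendment with IRB/IEC review under Section 9.1.1, which can be carried in the next planned amendment. The sponsor loses case-by-case discretion to dose a pregnant subject with BMS-986205, a discretion that Section 1.4.2 already speaks against.

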6.6 Overdose

An overdose is defined as the accidental or intentional administration of any dose of a product that is considered both excessive and medically important. Overdoses meeting the regulatory definition of SAE must be reported as an SAE (see [Section 6.1.1](#) for reporting details).

In the event of an overdose the investigator/treating physician should:

- 1) Contact the Medical Monitor/designee immediately
- 2) Closely monitor the subject for AEs/SAEs and laboratory abnormalities
- 3) Document the quantity of the excess dose as well as the duration of the overdosing in the CRF.

Decisions regarding dose interruptions or modifications will be made by the investigator in consultation with the Medical Monitor/designee based on the clinical evaluation of the subject.

6.7 Potential Drug-induced Liver Injury

Wherever possible, timely confirmation of initial liver-related laboratory abnormalities should occur prior to the reporting of a potential DILI event. All occurrences of potential DILIs, meeting the defined criteria, must be reported as SAEs (see [Section 6.1.1](#) for reporting details).

Potential DILI is defined as:

- 1) Aminotransaminases (ALT or AST) elevation > 3 times ULN
AND
- 2) Total bilirubin > 2 times ULN, without initial findings of cholestasis (elevated serum alkaline phosphatase)
AND
- 3) No other immediately apparent possible causes of aminotransaminases elevation and hyperbilirubinemia, including, but not limited to, viral hepatitis, pre-existing chronic or acute liver disease, or the administration of other drug(s) known to be hepatotoxic or biliary obstruction caused by tumor.

6.8 Other Safety Considerations

Any significant worsening noted during interim or final PEs, ECG, x-ray filming, or any other potential safety assessment required or not required by protocol should also be recorded as a nonserious AE or SAE, as appropriate, and reported accordingly.

7 DATA MONITORING COMMITTEE AND OTHER EXTERNAL COMMITTEES

Not applicable.

8 STATISTICAL CONSIDERATIONS

8.1 Sample Size Determination

8.1.1 *Dose Escalation (Part 1)*

As a Phase 1 dose escalation trial, the sample size at each dose in these arms depends on observed toxicity and posterior inference. For BMS-986205 in combination with nivolumab (with BMS-986205 lead-in), approximately 30 subjects are expected to be treated during the dose escalation phase. Initially, approximately 3 subjects will be treated at the starting dose levels of BMS-986205 in combination with nivolumab. Due to the potential for early discontinuation, an additional subject(s) may be enrolled to ensure approximately 3 evaluable subjects at each dose level.

During the dose escalation phase, once a dose level has been decided, a set of approximately 3 subjects will be treated at that specified dose level. Cohort-tolerability assessment and subsequent dose recommendation will occur when 2 evaluable subjects within a set have completed a 6-week DLT evaluation period (2 weeks of monotherapy lead-in plus 4 weeks of combination treatment). If the potential DLT occurring in any third evaluable subject regarding the specific dose level does not influence the dose recommendation by BLRM (-Copula), the BLRM (-Copula)-recommended next dose level may proceed without waiting for the third subject to complete the corresponding DLT observation period, after discussion and agreement between sponsor and investigators. Continuous re-assessment of dose recommendation by BLRM in the lead-in phase and BLRM-Copula in the combination phase will be carried out at each dose level.

Additional increments of approximately 3 evaluable subjects will be treated in recommended dose levels per BLRM-copula model during the dose escalation phase. At least 6 DLT-evaluable subjects will be treated in the selected dose cohort(s) chosen for expansion. Due to the BMS-986205 lead-in period, more than 3 subjects per cohort may be treated per BMS-986205 dose level considering potential DLTs happened within lead-in period.

Up to 12 additional subjects may be treated at any dose level below the estimated MTD/MAD for further evaluation of safety and pharmacodynamic/PK parameters as required.

8.1.2 Dose Expansion (Part 2)

Dose expansions of BMS-986205 administered in combination with nivolumab in 8 disease-restricted populations, and subjects in 1 mixed cohort of additional signal-seeking tumor types will be included. The following 7 tumor-specific cohorts will be classified into 3 categories according to different sample size modeling settings: SCCHN and bladder cancer in a group; cervical cancer, DLBCL, melanoma with prior anti-PD-(L)1 therapy, NSCLC with prior anti-PD-(L)1 therapy, and pancreatic cancer in a different group; and melanoma with prior anti-PD-(L)1 and anti-CTLA-4 therapy in another group. The two last groups will be analyzed using a Simon 2-stage design.

A Simon 2-stage (optimal) design will be used as a guide for many of the tumor-specific cohorts (see below for exceptions). The 2-stage design with a reasonable FPR and FNR, based on assumptions of true (target) and historic ORR for each indication, will provide guidance for the total sample size for these cohorts. The sample size and operational characteristics of using a 2-stage design are provided in [Table 8.1.2-1](#), although not used for hypothesis testing. For example, guided by, initially, a minimum of 10 subjects for the SCCHN tumor type will be treated in Stage 1 for an initial evaluation of efficacy. Assuming the true response rate is 50% when treated with BMS-986205 in combination with nivolumab, if there are 2 or fewer responses in 10 treated subjects, the cohort would likely not be considered as efficacious. The probability of early stopping for futility is approximately 53% in this case if in fact the treatment is ineffectual. The totality of efficacy data and response profile will be considered while making the decision to terminate. Enrollment will be continued during initial efficacy evaluation (ie, with the indicated number of subjects at Stage 1) to ensure that additional subjects are enrolled to account for unexpected trial impact, such as response non-evaluable subjects due to early drop-out, design parameter change (eg, historical rate update), and so on.

For an expansion cohort of approximately 35 subjects in the cervical, melanoma: prior anti-PD-(L)1, pancreatic, NSCLC: prior anti-PD-(L)1, and DLBCL cohorts, and an assumed true response rate of 30%, there is a 94% chance of observing at least 7 responses (in other words, the FNR is 6%). If the true response rate is only 10% rather than 30%, then there is a 6% chance that there will be at least 7 responses in 35 subjects (in other words, FPR is 6%). Also if 7 responses are observed (eg, 20% observed response rate), the lower bound of the 80% confidence interval (CI) for the ORR is 11% (higher than historical ORR of 10%). The CI is calculated using the Clopper-Pearson method.

For an expansion cohort of approximately 27 subjects in the bladder and SCCHN tumors and assumed true response rate of 50%, there is a 88% chance of observing at least 11 responses (in other words, the FNR is 12%). If the true response rate is only 25% rather than 50%, then there is a 5% chance that there will be at least 11 responses in 27 subjects (in other words, FPR is 5%). If 11 responses are observed (eg, 40% observed response rate), the lower limit of the 80% CI for the ORR is 28% (higher than historical ORR of 25%). The CI is calculated using the Clopper Pearson method.

For an expansion cohort of approximately 37 subjects with melanoma with prior anti-PD-(L)1 and anti-CTLA-4 therapy, and an assumed true response rate of 20%, there is a 85% chance of observing at least 5 responses (in other words, the FNR is 15%). If the true response rate is only 5% rather than 20%, then there is a 14% chance that there will be at least 5 responses in 37 subjects (in other words, FPR is 14%). Also, if 5 responses are observed (eg, 14% observed response rate), the lower bound of the 80% CI for the ORR is 7% (higher than historical ORR of 5%). The CI is calculated using the Clopper-Pearson method.

The Simon 2-stage design will not be used for the mixed cohort of additional signal-seeking tumor types in Part 2. Approximately 35 to 40 subjects will be enrolled to allow for the exploration of early efficacy signals seen during the dose escalation portion of the trial as well as potential signals arising from ongoing trials of other IDO1 inhibitors in combination with anti-PD-(L)1. A 2-stage design will also not be utilized for the RCC and I-O naïve melanoma and NSCLC cohorts, as nivolumab is already an established standard of care in these settings. Approximately 40 subjects will be enrolled in each of these cohorts to allow for the exploration of early efficacy signals of BMS-986205 in combination with nivolumab.

Approximately 16 melanoma I-O naïve BRAF mutant subjects' post-BRAF inhibitor therapy will be randomized into 2 cohorts and will either be treated with nivolumab or nivolumab in combination with BMS-986205, but will not be used for formal statistical comparison.

Table 8.1.2-1: Dose Expansion: Example of Simon 2-stage Design Characteristics

Expansion Cohort	Historic ORR (%)	Target ORR (%)	Stage 1 /Total N	Stage 1 Responses Futility Boundary	Alpha/Power (%)	Probability of Early Stopping (%)
Cervical, Melanoma: Prior anti-PD-(L)1, Pancreatic NSCLC: Prior anti-PD-(L)1, and DLBCL	10	30	12/35	1	10/90	66
Bladder and SCCHN	25	50	10/27	2	10/90	53
Melanoma: Prior anti-PD-(L)1 and anti-CTLA-4	5	20	12/37	0	10/90	54

*Note: For the melanoma, prior anti-PD-(L)1, and prior anti-PD-(L)-1/anti-CTLA-4 cohorts, the analysis will be focused on approximately 35 subjects who are BRAF (wild-type) WT.

Abbreviations: CTLA-4 = cytotoxic T lymphocyte-associated antigen 4; DLBCL = diffuse large B cell lymphoma; I-O = immuno-oncology; NSCLC = non-small cell lung cancer; PD-1 = programmed cell death; PD-L1 = programmed death receptor-ligand 1; PD-(L)1 = either PD-1 or PD-L1; ORR = objective response rate; SCCHN = squamous cell carcinoma of the head and neck..

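### Part 2 quotes 94% and 88% chances of reaching its response benchmarks without the Stage 1 futility stop that its own table assumes, and the tabled 10/90 belongs to cut-offs one response lower

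*Combined protocol and SAP*

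**What the plan says.** Section 8.1.2 and the synopsis (Sample Size Determination, Part 2) use Simon's optimal two-stage design as a guide for three groups of cohorts. Table 8.1.2-1, repeated as Table 3 in the synopsis, gives for each group the historic rate, target rate, Stage 1 n/total N, Stage 1 futility boundary, alpha/power and probability of early stopping:

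- cervical, pancreatic, DLBCL, and melanoma or NSCLC with prior anti-PD-(L)1: "10 30 12/35 1 10/90 66"
- "Bladder and SCCHN 25 50 10/27 2 10/90 53"
- melanoma with prior anti-PD-(L)1 and anti-CTLA-4: "5 20 12/37 0 10/90 54"

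The table has no column for the final cut-off.

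The text of 8.1.2 then gives benchmarks at full cohort size. For 35 subjects at a true rate of 30%, "there is a 94% chance of observing at least 7 responses (in other words, the FNR is 6" per cent); at a true rate of 10%, "there is a 6% chance that there will be at least 7 responses in 35 subjects". For 27 subjects at a true rate of 50%, "there is a 88% chance of observing at least 11 responses (in other words, the FNR is 12" per cent), with an FPR of 5% at 25%. For 37 subjects it gives 85% for at least 5 responses at 20%, with an FPR of 14% at 5%.

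On the Stage 1 rule, 8.1.2 works through SCCHN (2 or fewer responses in 10) and says: "The probability of early stopping for futility is approximately 53% in this case if in fact the treatment is ineffectual". It also says that the design is not used for hypothesis testing, that all efficacy data inform a decision to terminate, and that enrolment continues during the Stage 1 evaluation. On scope, after listing the three groups with SCCHN and bladder first, it says: "The two last groups will be analyzed using a Simon 2-stage design".

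**The concern.** The table and the text describe the same cohorts on different bases. The early-stopping probabilities and the 10/90 in the table assume that the Stage 1 boundary is applied. The 94% and 88%, and the false-negative rates taken from them, leave no room for a cohort to stop at Stage 1. A truly active cohort can fall at or below the boundary by chance, and that loss belongs in any false-negative rate quoted for the design.

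Without a final cut-off in the table, a reader will naturally attach the tabled 90% power to the benchmarks in the text (7, 11 and 5 responses). What is at stake is the description of how often an active combination would be missed, in a section that offers the FPR and FNR as the reason for the cohort sizes.

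**Working it through.** **Inputs.** All come from Table 8.1.2-1 and the text of 8.1.2: p0/p1 of 10/30%, 25/50% and 5/20%; n1/N of 12/35, 10/27 and 12/37; Stage 1 boundary r1 of 1, 2 and 0; text benchmarks r of 7, 11 and 5.

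**Step 1: reproduce the printed figures.** The single-stage tail is P(X ≥ r | N, p).
- P(X ≥ 7 | 35, 0.30) = 0.9350, printed as 94%; P(X ≥ 7 | 35, 0.10) = 0.0552, printed as 6%.
- P(X ≥ 11 | 27, 0.50) = 0.8761, printed as 88%; P(X ≥ 11 | 27, 0.25) = 0.0528, printed as 5%.

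The tabled early-stopping probabilities also reproduce as P(X1 ≤ r1 | n1, p0): 0.659, 0.526 and 0.540, printed as 66%, 53% and 54%.

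**Step 2: chance that an active cohort meets the futility boundary.** P(X1 ≤ r1 | n1, p1):
- 0.7^12 + 12 × 0.3 × 0.7^11 = 0.0138 + 0.0712 = 0.085 for the 35-subject cohorts.
- (1 + 10 + 45)/1024 = 0.055 for the 27-subject cohorts.

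Some of these cohorts would have missed the final benchmark anyway, so the loss of power is smaller than the stopping probability.

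**Step 3: apply the boundary and keep the text benchmarks.** The two-stage probability is the sum over x1 > r1 of P(X1 = x1) × P(X2 ≥ r − x1), with X2 from the remaining N − n1 subjects.

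| Benchmark | Printed FPR / chance | No Stage 1 stop | Boundary followed |
|---|---|---|---|
| ≥7/35 | 6% / 94% | 5.5% / 93.5% | 4.5% / 87.5% |
| ≥11/27 | 5% / 88% | 5.3% / 87.6% | 4.9% / 85.1% |
| ≥5/37 | 14% / 85% | 3.6% / 88.8% | 3.2% / 84.8% |

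Power falls by 93.5 − 87.5 = 6.0 points and by 87.6 − 85.1 = 2.5 points. In the 37-subject row, the printed 85% agrees with the two-stage value and not with the single-stage one, so neighbouring paragraphs use different bases. The printed 14% FPR in that row reproduces on neither basis.

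**Step 4: find the cut-offs that give 10/90.** With the tabled n1, N and r1, the requirement is met at these final cut-offs:
- ≥6/35: alpha 9.8%, power 90.1%
- ≥10/27: alpha 9.9%, power 90.4%
- ≥4/37: alpha 9.3%, power 90.2%

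A grid search for the design with the smallest expected sample size under p0 at 10/90 returns these same three designs.

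**Step 5: where the text benchmarks come from.** Lower limits of the 80% Clopper-Pearson interval:
- 7/35: 11.5%; 6/35: 9.3% (historic rate 10%)
- 11/27: 27.7%; 10/27: 24.4% (historic rate 25%)
- 5/37: 6.7%; 4/37: 4.8% (historic rate 5%)

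Each text benchmark is the smallest count whose lower limit exceeds the historic rate.

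**Step 6: scope of the two-stage design.** The sentence in 8.1.2 that names the last two groups leaves out SCCHN and bladder. The synopsis (Part 2: Dose Expansion) lists all three groups under the Simon design, section 3.1.6 gives SCCHN and bladder a Stage 1 of at least 10 subjects, Table 8.1.2-1 has a row for them, and the worked example in 8.1.2 is SCCHN.

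**The case against.** The strongest reply is that 94% and 88% are correct binomial probabilities for cohorts that reach 35 and 27 subjects, and that the text is worded for cohorts of about that size. That stands: these are not arithmetic slips. The fault is in calling their complements the FNR beside a table built on a futility stop.

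The second reply is that the boundary does not bind. Crossing it makes a cohort only likely to be judged inactive, all efficacy data are weighed, Stage 1 sizes are minimums, and enrolment continues meanwhile. This also stands, and it limits the point. A reader might infer that the trial's actual power is 87.5% and 85.1%. The documents do not support that, because those values need the boundary to be followed every time; they are the lower ends of ranges. Equally, 93.5% and 87.6% need it never to be followed, whereas the tabled 10/90 and early-stopping probabilities need it always to be followed.

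The third reply is that the higher text benchmarks have a purpose. They do, as the 80% interval criterion shows. A reader might infer that 7, 11 and 5 are mistakes for 6, 10 and 4, or that the tabled design fails its 10/90. Neither follows: the design meets 10/90 at its own cut-offs, and the benchmarks answer a different question. What is missing is a statement that the two sets differ.

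**Conclusion.** The stated false-negative rates and the tabled power do not describe one design. With the text benchmarks:

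- 35-subject cohorts: power between 87.5% (boundary always followed) and 93.5% (never followed), so an FNR of 6.5% to 12.5% against the stated 6%, and an FPR of 4.5% to 5.5%.
- 27-subject cohorts: power between 85.1% and 87.6%, so an FNR of 12.4% to 14.9% against the stated 12%, and an FPR of 4.9% to 5.3%.

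Against the tabled 90%, the gap with the boundary followed is 2.5 points at 35 subjects and 4.9 points at 27. These ranges assume independent responses at the stated rates and a Stage 1 look at exactly 12 or 10 subjects; a later look would change the lower ends.

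A reader might infer that the FNR is roughly doubled throughout, or that the cohorts are too small. The doubling is the worst case for the 35-subject group only. The protocol also tests no formal hypothesis (section 1.2) and reports ORR with an exact 95% interval (section 8.4.2), so no N, test or analysis depends on these figures. Severity is minor to moderate: a correction to stated operating characteristics.

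**What to change.** 1. In 8.1.2 and the matching synopsis paragraphs, give both bases as FPR/power. Boundary followed: 4.5%/87.5% (≥7/35), 4.9%/85.1% (≥11/27), 3.2%/84.8% (≥5/37). No Stage 1 stop: 5.5%/93.5%, 5.3%/87.6%, 3.6%/88.8%. Say that the boundary is guidance, so actual values lie between the two. This also replaces the 14% FPR in the 37-subject paragraph.
2. Add a final cut-off column to Table 8.1.2-1 and Table 3 (≥6/35, ≥10/27, ≥4/37 for 10/90). State that the text benchmarks are one response higher because they are set by the 80% interval criterion. Changing only the power entries would not do, because alpha 10% would then sit beside benchmarks whose alpha is 4.5%, 4.9% and 3.2%.
3. Reconcile the sentence in 8.1.2 about the last two groups with the synopsis, section 3.1.6 and Table 8.1.2-1, which apply the two-stage design to all three groups.

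The cost is a text and table correction, with somewhat less favourable stated power. Sample sizes, benchmarks and analyses stay as they are.
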